The aim of this study is to determine the efficacy of Sancuso® (granisetron transdermal system) 3.1 mg/24 hours in improving symptoms of nausea and vomiting in patients with gastroparesis. This will be a prospective open-label study using Sancuso® to treat symptoms of nausea and/or vomiting in patients diagnosed with gastroparesis. Symptomatic patients with diabetic or idiopathic gastroparesis with nausea and/or vomiting will be enrolled. The Gastroparesis Cardinal Symptom Index Daily Diary (GCSI-DD) will be used to capture the severity of symptoms, including nausea and vomiting, at baseline for one week. Patients will then be treated with Sancuso[®]. Patients will continue to fill out the GCSI-DD on a daily basis while undergoing treatment with Sancuso® for two weeks. To determine if Sancuso® treatment helps improve symptoms of nausea and vomiting, the symptoms at baseline will be compared to symptoms after the first week and the second week of treatment. Thirty patients diagnosed with gastroparesis (approximately 15 with diabetic and 15 with idiopathic gastroparesis) will be treated on an open label basis with Sancuso®. The goal of this study is to demonstrate the efficacy of Sancuso® in treating nausea and/or vomiting in gastroparesis patients. Safety information will also be collected regarding any adverse effects. If the results are encouraging, as we expect them to be based on personal experience, a larger double blind study would be appropriate.

2) Protocol Title

Sancuso® in patients with nausea and/or vomiting from gastroparesis: An open label study.

3) IRB Review History

No prior IRB submission

4) Investigator

[name]; Temple University Hospital; GI Section; [name]; [contact]; Email: [contact]

5) Objectives

The aim of this study is determine the efficacy of Sancuso® in improving symptoms of nausea and vomiting in patients with gastroparesis.

The specific objectives of this study are to determine:

1) Determine the treatment response of Sancuso® in gastroparetic patients with nausea and/or vomiting.

2) Determine which specific symptoms of gastroparesis improve – nausea, vomiting, early satiety, abdominal distension, abdominal pain

3) To determine symptomatic responses in both diabetic and idiopathic gastroparesis

4) To determine the time course of symptom improvement (with Sancuso® for symptoms of gastroparesis;

The hypotheses to be tested include:

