- 1) Sancuso® improves symptoms of gastroparesis.
- 2) Symptoms of nausea and vomiting improve to a greater degree than abdominal pain.

3) The beneficial response of Sancuso® is seen in both diabetic and idiopathic gastroparesis.

4) The symptom reduction occurs on days 3 after starting treatment and continues throughout the treatment course.

Sancuso in patients with nausea and/or vomiting from gastroparesis: An open label study. Page 2

6) Background

Gastroparesis is a chronic, symptomatic disorder characterized by delayed gastric emptying in the absence of mechanical obstruction. There is a common association with longstanding diabetes, which comprises a majority of gastroparesis cases. Idiopathic gastroparesis represents another common form.

Symptoms of gastroparesis can be debilitating, causing frequent hospitalizations and diminished quality of life. Major symptoms of gastroparesis include nausea, early satiety, bloating and vomiting. Although symptoms have been difficult to associate with delayed gastric emptying, nausea and vomiting are two symptoms that appear to relate to gastric retention. Nausea is among the most commonly reported symptoms in gastroparesis. In a recent study by Anaparthy et al, nausea was one of the most prevalent symptoms, reported in 96% of patients undergoing evaluation for gastroparesis. Nausea and vomiting also have a major impact on the reduction in quality of life that occurs in gastroparesis.

Treatment of gastroparesis involves the use of prokinetic agents and antiemetic agents. Prokinetic agents are used to accelerate gastric emptying and include metoclopramide, a dopamine type 2 receptor antagonist. Antiemetic agents are used to reduce nausea and vomiting and include Compazine and Phenergan. Recently, the 5HT3 receptor antagonists, such as ondansetron and granisetron have been used.

Sancuso® is a topical formulation of the 5HT3 receptor antagonist granisetron. The patch provides treatment for prevention of chemotherapy induced nausea and vomiting; the patch can be left in place for 7 days. The PI has used this in some patients to help improve the symptoms of nausea and vomiting in patients with gastroparesis. It is particularly helpful in patients with symptoms, such as vomiting, which precludes oral ingestion of an antiemetic. In addition, it is helpful when repeated doses of oral ondansetron or oral granisetron are needed to control symptoms.

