Descriptive analysis of the outcome variables will be constructed. Statistical analysis will be performed using SPSS. This study is designed to test the hypothesis that Sancuso® treatment provides improvement of gastroparetic symptoms. We will compare the absolute GCSI symptom scores before and after treatment using ANOVA for repeated measures. The symptom score improvement will be tested between the two treatment groups (diabetic and idiopathic gastroparesis) using ANOVA for repeated measures on ranks. Linear regression will be used to identify potential predictors of a beneficial symptomatic response to treatment.

Sample Size Determination

In a gastroparesis study at our institution with similar inclusion criteria, the average GCSI of 16 patients was 34.8 with standard deviation of 4.6. In a previous study at our institution, the absolute magnitude of symptom improvement for open label botulinum toxin was 38% (Miller 2002). The sample size in this study is calculated to show a benefit of Sancuso® by at least 30% reduction in the GCSI score. Assuming a standard deviation of 5 in the GCSI reduction of symptoms and with an α = .05 and β = .80, fifteen patients will be needed. We will recruit 15 diabetic patients and 15 idiopathic patients to enter this study to give adequate power to address the primary outcome variable - symptom response.

j) Confidentiality

Private health information (PHI) as defined by HIPAA will be collected as part of the research. These include: name, birthdate, telephone number, medical record number. All data will be kept confidential. Data will be entered into an Excel spreadsheet in an encrypted password protected computer accessible only be the study coordinator and the PI. The data will be deidentified.

k) Provisions to Monitor the Data to Ensure the Safety of subjects

This study involves minimal risk to the subjects. Patients will be monitored during the study in weekly study visits. The Sancuso® patch is being used to try to help reduce their symptoms of nausea and/or vomiting. The study is to allow recording of the response to treatment. All data will be kept confidential. Data will be entered into an Excel spreadsheet in an encrypted password protected computer accessible only be the study coordinator and the PI.

I) Withdrawal of Subjects

Patients have the option to not participate. Patients may elect at any time to stop treatment with Sancuso®.

11) Risks to Subjects

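### Hypothesis 3, benefit in both diabetic and idiopathic patients, has no within-etiology estimate or test in the analysis plan; the only etiology analysis compares the groups with each other (minor)

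*Combined protocol and SAP*

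**What the plan says.** Section 5 (Objectives) sets as specific objective 3 "To determine symptomatic responses in both diabetic and idiopathic gastroparesis", and lists as hypothesis 3 that "The beneficial response of Sancuso® is seen in both diabetic and idiopathic gastroparesis". Both concern response in each etiology.

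Section 10(i), Data Analysis, names four things:

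- A descriptive analysis, not stated to be by etiology.
- A before/after comparison: "We will compare the absolute GCSI symptom scores before and after treatment using ANOVA for repeated measures". No etiology factor or stratum is mentioned.
- One etiology analysis: "The symptom score improvement will be tested between the two treatment groups (diabetic and idiopathic gastroparesis) using ANOVA for repeated measures on ranks".
- A regression: "Linear regression will be used to identify potential predictors of a beneficial symptomatic response to treatment". The predictors are not listed.

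Sample Size Determination, in the same section, first says "fifteen patients will be needed" and then "We will recruit 15 diabetic patients and 15 idiopathic patients to enter this study to give adequate power". On timing, the opening summary says that "the symptoms at baseline will be compared to symptoms after the first week and the second week of treatment", and names neither week as the main one.

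**The concern.** A claim of benefit in both groups is a claim about two changes from baseline, one per etiology. The planned etiology analysis is about the difference between those two changes. The difference is zero when both groups improve equally and also when neither improves, so its result cannot settle hypothesis 3.

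The pooled before/after test helps, because it separates benefit in both from benefit in neither. Two situations are left over:

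- **Only one group benefits, and moderately.** The pooled test may be significant and the etiology test not, and the report may then say that both etiologies benefit.
- **Both groups benefit, but unequally.** The etiology test may be significant and be taken as evidence against a hypothesis that is true.

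Recruiting 15 of each etiology, right after saying that fifteen are needed, suggests that an analysis within each group was intended. The analysis text does not state one.

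**Working it through.** **Inputs from section 10(i).** Baseline mean GCSI 34.8; target reduction 30%; SD of the reduction 5; α = .05 (taken as two-sided, since the plan does not say); β = .80 (read as 80% power); 15 patients per etiology. Planned benefit: 0.30 × 34.8 = 10.44 points.

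**Assumed, not in the documents.** Smaller benefits of 5.22 points (half of 10.44) and 4 points; SDs of 7.5 and 10; normally distributed changes; one post-treatment change per patient.

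**The plan's own figure.** For a paired comparison, n = [(1.96 + 0.84) × 5 / 10.44]² = 1.8, so 2 patients by the normal approximation and 5 by the t distribution. The stated 15 is not reproduced. That does not affect this point, except to show that 15 per etiology is ample on the plan's inputs.

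**Within one etiology, n = 15, SD 5.** The 95% CI half-width is 2.145 × 5/√15 = 2.77 points. For 10.44 points the noncentrality is 10.44 × √15 / 5 = 8.09, and power exceeds 99.9% in each group and for both jointly.

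**Between etiologies, 15 v 15, SD 5.** The standard error is 5 × √(2/15) = 1.826. A difference of 5.22 gives noncentrality 5.22 / 1.826 = 2.86 and power 79%. A difference of 10.44 gives 5.72 and power 99.98%. Power of 80% needs a difference of 5.3 points.

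**Joint behaviour** (simulation, 100,000 trials per row, SD 5). The misleading-pair column is the share of trials with pooled improvement significant and the t test between etiologies not significant. The last column is the share in which both within-etiology 95% CIs lie above zero.

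| True benefit, group A / group B | Etiology test significant | Pooled significant, etiology not | Both CIs above zero |
|---|---|---|---|
| 0 / 0 | 5% | 2.3% | under 0.1% |
| 10.44 / 10.44 | 5% | 95% | 100% |
| 10.44 / 0 | 99.98% | 0.02% | 2.5% |
| 5.22 / 0 | 79% | 16% | 2.3% |
| 4 / 0 | 56% | 23% | 2.1% |
| 10.44 / 5.22 | 79% | 21% | 96% |

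In the 10.44 / 10.44 row that pair is the right answer; in the 10.44 / 0, 5.22 / 0 and 4 / 0 rows it is misleading.

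The plan's test is on ranks. With a rank test on the change scores (Mann-Whitney, 20,000 trials), the pair occurs in 0.06% (10.44 / 0), 18% (5.22 / 0) and 25% (4 / 0), and the etiology test is significant in 76% at 10.44 / 5.22. The picture is the same.

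**Larger assumed SDs.** The misleading pair occurs in 4% (10.44 / 0) and 23% (5.22 / 0) at SD 7.5, and in 16% and 19% at SD 10.

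**What the both-intervals rule costs.** Let p be the power in one group for a true benefit of 5.22. Both pass with probability p², and exactly one passes with probability 2p(1 − p).

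| SD | p | Both pass | Exactly one passes |
|---|---|---|---|
| 5 | 0.964 | 93% | 7% |
| 7.5 | 0.708 | 50% | 41% |
| 10 | 0.469 | 22% | 50% |

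With equal true benefit and a larger SD, one significant and one non-significant group is therefore a common chance result. The added text must warn against reading it as a difference.

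**The case against.** The strongest reply is that the harm is negligible on the plan's own inputs: with 10.44 points and SD 5, a benefit confined to one group is mistaken for benefit in both in 0.02% of trials. That stands. The 16% and 23% figures rest on smaller effects that I assumed, and the 4% at SD 7.5 and 16% at SD 10 for a full-size one-group benefit rest on SDs that I assumed. It is also fair that 15 + 15 recruitment points to an intended within-group reading, that this is a 30-patient uncontrolled study meant to inform a larger one, and that the plan nowhere says a non-significant etiology difference will be read as benefit in both.

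What remains is that a hypothesis listed for testing has no stated analysis that addresses it. An intention inferred from the sample-size paragraph names no score, week or criterion.

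A reader might also infer that the rank procedure is wrong or unusable as described. The documents do not support that. The sentence is about improvement between groups, which already points to change over time; what is left open is detail. The planned comparison need not be replaced by another test.

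**Conclusion.** The gap is real and minor. The plan states a between-etiology comparison where hypothesis 3 needs an estimate of change in each etiology. On the plan's inputs the stated analyses seldom mislead when only one group benefits. Under assumed smaller one-group effects (4 to 5.22 points, SD 5) they point the wrong way in about 16% to 23% of trials. With unequal benefit (10.44 v 5.22) the etiology test is significant in about 79%, although both intervals lie above zero in 96%.

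These figures apply to GCSI total, a secondary outcome. No SD is given for the primary GCSI-DD nausea/vomiting score, so the size of the problem there is unknown. A reader might infer that the main before/after analysis is compromised; it is not, because this point concerns only hypothesis 3 and objective 3.

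**What to change.** Keep the pooled before/after ANOVA and the planned between-etiology comparison, and add to Data Analysis in section 10(i):

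> For the GCSI-DD nausea/vomiting score (primary) and the GCSI total score, the mean change from the baseline week to treatment week [to be named in advance] will be estimated within each etiology with a 95% CI. Hypothesis 3 will be judged on the two within-etiology estimates for the primary score, and is supported if both CIs exclude zero in the direction of improvement. The between-etiology difference in change will be reported with a 95% CI as exploratory. Neither a non-significant difference, nor significance in one etiology and not the other, will be read as evidence of similar or different benefit.

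The investigator must name the week, since the summary uses both. I put the rule on the primary score so that it can be carried out as written; GCSI total could be chosen instead, but one score should be named.

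The cost is wording only: same patients, data and software. There are two downsides. Both groups of 15 must succeed: on GCSI total with a true 5.22 points in each, that happens in about 93%, 50% and 22% of trials at SD 5, 7.5 and 10, and the chance on the primary score is unknown. And without a control group the intervals show change from baseline, not a drug effect, so a supported hypothesis 3 should be reported in those terms.

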The Gastroparesis Cardinal Symptom Index (GCSI) is a validated patient-reported outcome for gastroparesis using a two-week recall period. The nine symptom GCSI (nausea, vomiting, retching, stomach fullness, unable to finish a meal, feeling excessively full after meals, loss of appetite, bloating, belly visibly larger) is based on three subscales (postprandial fullness/early satiety, nausea/vomiting, and bloating). A larger symptom questionnaire, the Patient Assessment of GI Symptoms (PAGI-SYM) includes the 9 symptoms in the GCIS, and additional symptoms of gastroesophageal reflux disease and functional dyspepsia. A daily diary form of the GCSI has been developed (GCSI-DD) includes symptoms relevant to patients with gastroparesis, captures daily variability of those symptoms and has psychometric properties consistent with a good patient-reported outcome endpoint for gastroparesis clinical trials. Each of these questionnaires, the PAGI-SYM, the GCSI, and the GCSI-DD are in the public domain for use by investigators and physicians.

7) Setting of the Human Research

Patients are seen for clinical care by [name] in the third floor of the Ambulatory Care Center of Temple University Hospital. For patients with refractory symptoms of nausea and/or vomiting from their gastroparesis, which comprise many of [name] patients, other offlabel treatment options are discussed including the use of tricyclic antidepressant agents as symptom modulators, botulinum toxin injection into the pylorus, gastric electric stimulation, and more recently the use of Sancuso® (granisetron transdermal system). If it is elected to proceed with Sancuso® for their clinical care, then the patients will be approached about participating in this open label study which will be recording their response to treatment.

The clinical nurse practitioner, [name], has an office in the GI Section where she will see patients in this study. Patients will be seen in five visits for this study.

Sancuso in patients with nausea and/or vomiting from gastroparesis: An open label study. Page 3

8) Resources Available to Conduct the Human Research

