Visit 4: Patients will be seen after the second one week of treatment. The GCSI daily diaries will be collected. The therapeutic response of the patients will be enquired using the simple Clinical Patient Grading Assessment Scale (CPGAS). Patients will fill out the Patient Assessment of GI Symptoms (PAGI-SYM), SF-36, HAD questionnaire, a modified McGill Pain

inventory, and a symptom side effect questionnaire. Patients will stop treatment with Sancuso® at this time, and be followed for an additional week of treatment off medication. Patients will continue to fill out the GCSI-DD on a daily basis and not take any 5-HT3 receptor antagonist. A follow up appointment in one week will be scheduled.

Visit 5: Patients will be seen after one week after cessation of treatment. The GCSI daily diaries will be collected. Patients will fill out the symptom side effect questionnaire. After this visit, the study period is over and the patient returns to clinical care.

f) Study Endpoints

Primary and Secondary Endpoints:

Primary:	Nausea and Vomiting severity scores using the GCSI-DD
Secondary:	Total Gastrointestinal Cardinal Symptom Index
-	Clinical Patient Grading Assessment Scale (CPGAS)

Patients will fill out daily information of their symptoms of gastroparesis using the Gastroparesis Cardinal Symptom Index Daily Diary (GCSI-DD). The Gastroparesis Cardinal Symptom Index (GCSI) is a validated patient-reported outcome for gastroparesis daily recording of symptoms. Several symptoms of gastroparesis including nausea, vomiting, retching, stomach fullness, unable to finish a meal, feeling excessively full after meals, bloating, belly visibly larger will be monitored. This is used in clinical practice and will be performed in this project.

For this study, the therapeutic response of the patients will also be enquired using the simple Clinical Patient Grading Assessment Scale (CPGAS). Patients will be asked if they improved, stayed the same, or worsened with Sancuso® treatment. The clinical response of their gastroparesis symptoms to Sancuso treatment with gradations from (+7) = completely better; (0) = no change, and (-7) = very considerably worse. Responders are defined as those with score of >0 and non-responders with score of \leq 0 by CPGAS. Patients will be asked if they experienced any side effects with Sancuso® treatment and to describe any side effects. Other than your GI symptoms, how have you been feeling?

Adverse events will be recorded.

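### The stated 15 patients does not follow from the plan's own inputs (a paired test against zero change needs 5), and power for the primary nausea/vomiting score is undocumented

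*Combined protocol and SAP*

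**What the plan says.** All the inputs are in section 10(i), under Sample Size Determination. For the baseline, an earlier study at the institution is cited in which "the average GCSI of 16 patients was 34.8 with standard deviation of 4.6". The paragraph also cites an earlier open-label result: "the absolute magnitude of symptom improvement for open label botulinum toxin was 38" percent. The design target is "calculated to show a benefit of Sancuso® by at least 30% reduction in the GCSI score". The variability is set by "Assuming a standard deviation of 5 in the GCSI reduction of symptoms". The conclusion is "with an α = .05 and β = .80, fifteen patients will be needed".

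The plan then recruits 15 diabetic and 15 idiopathic patients "to give adequate power to address the primary outcome variable - symptom response". It does not name the test used for the calculation, whether it is one- or two-sided, the null value or any allowance for dropout. The Data Analysis paragraph plans a before-and-after comparison by repeated-measures ANOVA.

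Section 10(f), Study Endpoints, gives the primary endpoint as "Nausea and Vomiting severity scores using the GCSI-DD" and lists the total index as secondary. The Outcome measures paragraph in 10(i) agrees. Section 6, Background, describes the full instrument: "The nine symptom GCSI (nausea, vomiting, retching, stomach fullness, unable to finish a meal" and four further symptoms, in three subscales, one of which is nausea/vomiting.

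**The concern.** There are two separate problems.

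First, the stated effect is very large relative to the stated SD, so a before-and-after test in one cohort should need only a handful of patients. A figure of 15 suggests either that the inputs printed are not the ones used, or that the hypothesis being sized is not the one a reader would assume. Because the null value is missing, a reader cannot tell whether the trial was sized to show any improvement or to show an improvement of more than 30%. With 15 patients these are very different propositions. In a single-arm study, a significant change from baseline could also be misread as demonstrating the 30% benefit named in the paragraph.

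Second, the calculation is on a score called only GCSI, yet the power is claimed for the primary outcome, which is the daily-diary nausea/vomiting score. If the two are different scores, the claim does not follow from the calculation.

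The β of .80 is a minor slip: power of .80 (β = .20) is almost certainly meant.

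**Working it through.** **Inputs, all from Sample Size Determination in 10(i).** Mean GCSI 34.8; target reduction 30%; SD of the reduction 5; α = .05. Power is taken as .80. Sidedness is not stated; two-sided is the base case and one-sided is also shown. Power is computed from the noncentral t distribution with n − 1 degrees of freedom and noncentrality d√n.

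**Step 1: try to reproduce 15, test against zero change.**
- Reduction: 0.30 × 34.8 = 10.44 points.
- Standardised effect: d = 10.44 / 5 = 2.088.
- Normal approximation: n = ((1.960 + 0.842) / 2.088)² = 1.8, rounded up to 2.
- Paired t, exact:

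| n | Two-sided power | One-sided power |
|---|---|---|
| 3 | 49.8% | 74.0% |
| 4 | 78.7% | 92.7% |
| 5 | 92.9% | 98.2% |
| 15 | >99.99% | >99.99% |

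The requirement is 5 patients two-sided, or 4 one-sided. For 15 to be the two-sided answer at 80% power, the SD of the reduction would have to be 10.44 / 0.778 = 13.4 rather than 5.

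**Step 2: other readings of the same inputs.**
- β = .80 taken literally (20% power): 3 patients two-sided, already with 49.8% power.
- 90% or 95% power, two-sided: 5 or 6 patients.
- 5 read as the SD at each time point with zero correlation (SD of change 5√2 = 7.07): 6 patients.
- Two-sample t test: 5 per group.

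**Step 3: read the target as showing a reduction greater than 30%.** This needs a true value above 30%. The only candidate in the paragraph is 38%, which the plan does not call its design effect.
- Margin: (0.38 − 0.30) × 34.8 = 2.784 points; d = 2.784 / 5 = 0.557.
- Two-sided: 27 patients give 79.5% and 28 give 81.1%, so 28 are needed.
- One-sided: 21 give 79.4% and 22 give 81.1%, so 22 are needed.
- With 15 patients, power is 52% two-sided and 66% one-sided. With 30 it is 84% and 91%.

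The nearest variant found is 17 patients. It uses this 30% null, a one-sided test, the normal approximation and the baseline SD of 4.6 in place of the stated 5. It discards a stated input and is still not 15.

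**Step 4: what the enrolled size delivers** (two-sided .05, 80% power, null of zero change, complete data; points and percentages use SD 5 and mean 34.8).

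| n | Detectable change | In points | As % of 34.8 | 95% CI half-width, t × 5/√n | Observed reduction needed for the CI to exclude 30% |
|---|---|---|---|---|---|
| 15 | 0.778 SD | 3.9 | 11% | 2.77 | (10.44 + 2.77) / 34.8 = 38.0% |
| 30 | 0.529 SD | 2.6 | 7.6% | 1.87 | (10.44 + 1.87) / 34.8 = 35.4% |

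**Step 5: which score is 34.8?** Over nine items it is 34.8 / 9 = 3.9 per item. Over nausea, vomiting and retching it would be 34.8 / 3 = 11.6 per item. The nine-item sum is the plausible reading, but this is an inference: the paragraph does not say, and the documents give no item scale. Neither the protocol nor the SAP text gives a mean, an SD of change or a target change identified as belonging to the GCSI-DD nausea/vomiting score.

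**The case against.** The strongest reply is that 5 belongs to a paired t test that the plan does not name. The planned analysis is a repeated-measures ANOVA, with time points and multiplicity unspecified, so the fair statement would be that 15 cannot be reproduced, not that 5 is correct. This stands as a limit on wording: 5 holds only for the test against zero change. It does not rescue 15, because even at a two-sided α of .001 a paired t test needs only 9 patients (80.8% power).

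The 30% null is also a secondary reading. The Data Analysis paragraph says the hypothesis is that treatment improves symptoms, which points to zero change, and the 38% comes from a different treatment. That is fair. The reading is included because the wording of the target permits it, and because it too fails to give 15.

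Fifteen per etiology may simply have been a practical number that suits the aim of showing response in both groups. That is reasonable for a small open-label study meant to inform a larger blinded one, but the paragraph presents the number as calculated.

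Finally, the mismatch of scores rests partly on inference. True, but whichever score 34.8 belongs to, nothing ties these inputs to the primary endpoint.

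**Conclusion.** The concern holds. The stated 15 does not follow from the plan's inputs under any reading tried: 5 patients for a two-sided paired test against zero change, 28 two-sided or 22 one-sided for a test against 30% with a true 38%. The power asserted for the primary outcome is undocumented.

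The consequence is limited. Against zero change the discrepancy runs towards more patients than needed, so enrolment is not endangered, and nothing here shows the trial to be underpowered. What is wrong is the stated justification: it cannot be checked, and it does not tell the reader what the trial can detect on its primary outcome. It should be fixed, but it does not threaten the study.

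The conclusion rests on reading β of .80 as power of .80, on 5 being the SD of the within-patient change as the text says, and, for the score mismatch only, on 34.8 being the nine-item total.

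**What to change.** Reword the Sample Size Determination paragraph:

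1. Keep 15 diabetic and 15 idiopathic patients.
2. Write power = .80 (β = .20), two-sided α = .05, and name the test and its null value of zero change.
3. Replace the sentence deriving 15 with what the sample delivers: a within-patient change of 0.78 SD with 15 per etiology and 0.53 SD with all 30, assuming complete data. At SD 5 these are 3.9 and 2.6 GCSI points. State the dropout allowance, or that there is none.
4. Say which GCSI score the 34.8 refers to.
5. Express the calculation on the primary GCSI-DD nausea/vomiting score, using an SD of change from the institution's earlier data if available and otherwise an assumed range. If nausea and vomiting are separate primary scores, as the plural in the endpoint allows, do this for each. Purely as an illustration, with an assumed SD of change of 0.5 to 1.5 points, the detectable change is 0.39 to 1.17 points with 15 and 0.26 to 0.79 with 30.
6. State that a significant result against zero does not by itself show a 30% reduction, and report the estimated reduction with its 95% CI.

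The cost is one paragraph of text and a less specific justification. Enrolment, visits and endpoints do not change.
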